The objective of this proposed study is to build upon these promising R21 findings by testing whether HCEM, a computer-delivered SBI that simultaneously targets STI risk and alcohol/drug use during pregnancy, reduces antenatal and postpartum risk more than an attention, time, and information matched control condition among pregnant women seeking prenatal care. To meet this objective, we propose a two-group, randomized controlled trial in which a racially diverse sample of 250 pregnant women at risk for STIs and alcohol/drug use are recruited from high-volume prenatal care clinics or through telephone and online methods, and are assigned to either (a) a computer-delivered, single-session brief intervention plus two booster sessions; HCEM; or (b) a computer-delivered control condition. Computer and/or phone-delivered follow-up assessments will occur at 2 and 6 months, and extending to 6-weeks postpartum. Our biometric objective measures include STI incidence (e.g., chlamydia, gonorrhea) and birth outcomes. We propose the following Specific Aims:

Aim 1 (Primary outcomes): To test the hypothesis that HCEM, compared to an attention, time and information matched control condition, will reduce risk of STIs and alcohol/drug use among at-risk pregnant women during pregnancy at 2 and 6-months follow-up.

- (a) HCEM, as compared to control, will result in fewer unprotected sexual occasions;
- (b) HCEM, as compared to control, will result in lower alcohol use and illicit drug use, and fewer heavy episodic drinking days.

Aim 2 (Secondary outcomes): To test the hypothesis that HCEM will be associated with key secondary outcomes:

- (a) HCEM, as compared to control, will result in fewer STIs (re-infection and/or new infections) during pregnancy and at 6-weeks postpartum;
- (b) HCEM, as compared to control, will result in fewer unprotected sexual occasions and lower alcohol use and illicit drug use at 6-weeks postpartum;
- (c) HCEM, as compared to control, will result in better birth outcomes (e.g., low birth weight);
- (d) To collect and measure resource utilization and costs of HCEM to provide preliminary data to assess feasibility for future implementation and dissemination and to inform practice guidelines.

Aim 3 (Mediation): To explore direct and indirect effects in the above hypotheses:

- (a) To explore the effect of HCEM on the intermediate outcomes of pregnancy-specific knowledge and risk perceptions, autonomous motivation and self-efficacy during pregnancy;

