4.0. Approach

[figure not shown]
The proposed study is a two-group, randomized, controlled design with an initial session (conducted close to the first prenatal visit), plus two booster sessions within one month later (at 2 and 4 weeks). There will be follow up assessments at 8 and 24 weeks, and at 6 weeks postpartum, conducted by computer and delivered by RA either at the clinic, or remotely over the telephone, or at participants' home. Birth outcome data will be available by postpartum medical records. We will focus on testing the efficacy and utility of the theoretically driven HCEM to target STI risk during pregnancy and postpartum, integrating alcohol and drug use given the well-supported relationship between these risks. The proposed study will use a sophisticated intervention development tool, the Computerized Intervention Authoring Software (CIAS). A technology-delivered intervention approach promotes scientific rigor and greatly facilitates replicability in the community.

4.1. The Health Check-up for Expectant Moms (HCEM) is a brief intervention (one session plus two booster sessions) that is theory-driven and derived from empirical support (see Figure 2, below). Motivational interviewing (MI) has been found to be effective for STI/HIV risk reduction. MI is an intervention approach with wide dissemination and demonstrated efficacy. Consistent with the Self Determination Theory (SDT), MI is a client-centered counseling style that facilitates internal motivation to change through alignment of behavior change with deeply held beliefs,

values, and goals. MI utilizes evolving readiness and self-efficacy to change.

Moreover, the MI model appears to be generalizable to different populations, including low-income urban women. The components of the STI and alcohol/drug use risk reduction to be used in HCEM are formulated to be highly specific to the perinatal setting and entail

Figure 1. Conceptual Model of HCEM Effects and Mechanisms

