5.1. Inclusion/exclusion criteria: Participants will be 250 pregnant women (as close as possible to first prenatal visit), age 18 or older, and will follow similar recruitment to the R21 study given feasibility and acceptability rates. Specifically, the study will include pregnant women who endorse: 1) at least one unprotected vaginal (or anal) sex occasion (USO) in the past 30 days (supported by the literature for our “high risk” sample, identified as such based on childbearing age, urban, ethnically diverse, and reporting co-morbid recent history of substance use), and 2) having more than one male partner in the last 6 months and/or having uncertainty about current sexual partner’s monogamy, and 3) current alcohol/drug use risk, 4) currently resides in the state of Michigan. Exclusion criteria include: 1) inability to provide informed consent (e.g., clear cognitive impairment), or 2) inability to understand English.

5.2. Recruitment: We successfully completed the R21 study in a prenatal clinic in Providence, Rhode Island. We will implement similar methods to recruit for the proposed study. Past year public health data reports increases in STI cases reported in Washtenaw County (Michigan). Recruitment will take place in a number of ways, including in-person at clinical sites within Michigan Medicine, other Michigan based clinics, or remotely. Remote recruitment for Michigan Medicine patients will happen by a member of the research team conducting a chart review (MiChart) and contacting prenatal patients over the phone, via physical mail, or through email messages. The research team will also recruit online by advertising on the University of Michigan Health Research website (<https://umhealthresearch.org>) or through social media platforms (e.g. Facebook, Instagram). Online/remote recruitment will not be limited to Michigan Medicine patients, however; pregnant women residing in the state of Michigan who are patients of outside

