In a Michigan Medicine clinic setting, those who express tentative interest in the screening survey will be directed to speak with the study RA to complete the short (10-15 minutes) computer-delivered health survey including questions to determine eligibility. Before completing the screening survey, they are given a copy of the screener consent, to which they must verbally agree to before proceeding. The computerized screening will use software delivered on an easy to use iPad iOS. The research team has used this procedure successfully to recruit this target population. In a remote setting, potential participants will complete the same screener online using their home computer, tablet or smart phone. The screener will include well-validated and recommended measures for this population. Women who score eligible on the screener in a clinic setting, will be informed by the RA about the clinical trial, and interested women will fill out a contact sheet and make an appointment for the baseline session. Before conducting the baseline session, the RA will explain the informed consent process as well as the study procedures, and ask comprehension questions before obtaining consent. Both the informed consent process and the baseline session will be conducted in a private room in the clinic (or a private room at the Department of Family Medicine office), providing a confidential and comfortable environment for the participant.

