Booster sessions can be completed by the participant in their home and accessed through our secure, HIPAA-compliant study website using either a computer or mobile device (see Fig. 3, above). The use of computer technology for gathering self-report data further enhances overall protection. This software utilizes SSL technology for encrypting of communications between remote computers and the server itself, is HIPAA-compliant, and is currently used in a number of major NIH-funded research studies, including those of the PI. Data will be encrypted in transit between user and server. Importantly, no identifying information will be entered into the CIAS software. Given the sensitive nature of this research, the computer software will simply generate a code number for each participant. Additionally, all forms with participant information will be marked with a code number and not with the participants' name. The link between the participant code number and name will be securely stored on the HIPAA-compliant database REDCap. This database will only be accessible by the Study Coordinator and Research Assistants.

[figure not shown]
In-person follow-up assessments will be completed at the clinic (Michigan Medicine) and scheduled with prenatal visits when possible. Given the current COVID-19 pandemic and

associated research restrictions, the follow-up assessments will be conducted remotely (August 2020 to present time, February 2023), both over the phone and online, using the CIAS software. The postpartum assessment will be conducted by the RA at a private and confidential location convenient to the participant (e.g., clinic, home, or remotely), coordinated with the timing of the postpartum medical visit, maximizing likelihood of completion.

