Screener items (embedded with general health questions):

1. Questions for history of STI sexual risk (i.e., number of occasions of condomless vaginal (and anal) sex in the past 30 days);
2. T-ACE (four questions) is a screen for risk drinking developed for use in OB/GYN settings;
3. Substance Use Risk-Profile Pregnancy Scale (SURP-P) (three questions) this screening is specifically designed to quickly identify obstetrical patients at risk for alcohol or illicit drug use.

Table 1. Study Measures		Antenatal		Postpartum
Self-report measures	Baseline	19-28 weeks	36-39 weeks	6 weeks
Demographic Information	X			
Marlowe-Crowne Social Desirability – Short Form	X			

Timeline Follow-back, sex, alcohol, drug use	X	X	X	X
Condom Use Self-Efficacy	X	X	X	X
Treatment Self-Regulation Questionnaire	X	X	X	X
HIV/STI Knowledge Questionnaire	X	X	X	X
Risk Perceptions Items (STI)	X	X	X	X
Importance, Readiness, and Confidence Rulers	X	X	X	X
Condom Attitude Scale	X	X	X	X
Perceived Competence Scale	X	X	X	X
COVID-19 Family Stress Screener	X	X	X	X
Objective biometric measures				
Urine or Vaginal Swab Collection: STI Testing	X*	X	X	X
Birth Outcomes				X
Hair Sample Testing (suspended 11/2022)	X**		X**	
Economic and implementation measures				
Costs Analysis	X	X	X	X
Clinic staff surveys	X			

*In-person, Michigan Medicine visits only.

**A urine sample may be collected in place of a hair sample in the event that a hair sample cannot be collected.

The following assessment measures will be administered at the baseline assessment:

1. Demographic information, including age, race, ethnicity, marital/partner status, parity, employment, socioeconomic status.
2. *Marlowe-Crowne Social Desirability Scale-Short*,¹¹⁴ includes 13 items sensitive to social desirability bias.

5.5.2 Primary Outcome Measure:

1. *Unprotected sexual occasions (USOs)* at the 8-week follow-up assessment.

USOs will be obtained from the *Timeline Follow-Back (TLFB)* to assess sex-risk behaviors at baseline and follow up assessments. The TLFB is a calendar assisted structured interview that provides a way to cue memory so that accurate recall is enhanced for event-level data; it has been used to assess sexual risk-taking. USOs will be assessed in the 90 days prior to the baseline, as well as the 8-week follow-up assessments.

5.5.3 Secondary Outcome Measures:

1. *Alcohol use and Illicit drug use*: Self-reported days of alcohol and illicit drug use at 8-week assessment.

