7.0. Data Analysis: Descriptive statistics will be calculated to summarize baseline characteristics for the full cohort and by intervention arm. Quality inspection will be carried out periodically to screen for missing-ness and data anomalies, and entry error. T-tests and chi-square-tests will be used to compare study arms with respect to demographic characteristics and baseline measures of unprotected sex and alcohol/drug use. Any identified confounders with $p \leq 0.10$ will be included in all subsequent analyses. Using the TLFB, we estimate the frequency of number of days in the 90-day period that the participant is engaged in a risky behavior. This will be carried out separately for each of the outcomes, namely, unprotected sex, illicit drug use and alcohol use, and heavy episodic drinking days (Hypothesis 1 and 2). The outcomes will be analyzed under a clustered count regression framework (Poisson or Negative Binomial) with frequency as outcome, and time (baseline, 2 months, 6 months), group (HCEM, control) and time-by-group interaction as the primary covariates. A generalized linear mixed models (GLIMMIX) approach will be adopted assigning a random subject intercept to account for the clustering within each participant. The regression model will be further controlled for potential confounders such as demographic characteristics, social desirability, and other variables that are identified to be significantly associated with outcome in the univariate analyses. We will adjust analyses for baseline pregnancy stage and assessment timing, as well as delivery status (delivered/not delivered) at follow up assessments in our data analysis, and pregnancy loss during course of study (e.g., miscarriage or stillbirth). Changes over time within each group will be estimated post-hoc by sliced effects derived from the regression model. In additional analysis, reduction in proportion of participants engaged in the risky behavior on ≥ 1 days within the 90-day period will be analyzed using a clustered logistic regression with a dichotomous outcome at the subject level indicating the status of the engagement, and with time (baseline, 2 months, 6 months), group (HCEM, control), time-by-group interaction as the primary factors. As before, a random subject intercept will account for the clustering and the model will be controlled for the same ensemble of covariates as in the case of the count regression models. Similar analyses will be conducted in the secondary aims for the outcomes that will be measured postpartum. To test hypothesis 3a and 3b, we will use structural equation modeling (SEM) approach. These include pregnancy-specific measures of autonomous motivation, self-efficacy, knowledge and risk perceptions (see Table 1). These measures are all continuous and will be measured at all three time points. All relevant direct and indirect effects will be evaluated. Significance of the indirect effect of the mediators will be tested using bootstrap method which appears to have good power in small samples. Birth outcome data will be available to the team by accessing patient medical records postpartum (Hypothesis 2c).

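### In the additional yes/no analysis of unprotected sex, the 90-day window at the first follow-up reaches 29 to 34 days before baseline, so near-schedule visits are almost all recorded 'yes' in both arms

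*Combined protocol and SAP*

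**What the plan says.** The yes/no outcome is defined in section 7.0, where the reduction in the proportion of "participants engaged in the risky behavior on ≥ 1 days within the 90-day period will be analyzed using a clustered logistic regression" is modelled with time (baseline, 2 months, 6 months), group and their interaction, and a random intercept per woman. The plan labels this an additional analysis. The primary outcome is the count of unprotected sexual occasions (USOs) at 8 weeks.

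The look-back is in section 5.5.2: "USOs will be assessed in the 90 days prior to the baseline, as well as the 8-week follow-up assessments".

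The visit schedule is in section 4.0: "There will be follow up assessments at 8 and 24 weeks, and at 6 weeks postpartum". Section 3.0 gives it in months: "follow-up assessments will occur at 2 and 6 months". Table 1 labels the first follow-up column 19 to 28 weeks. Section 5.4 adds: "In-person follow-up assessments will be completed at the clinic (Michigan Medicine) and scheduled with prenatal visits when possible".

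The entry rule in section 5.1 requires "at least one unprotected vaginal (or anal) sex occasion (USO) in the past 30 days". Screening and baseline can be separate occasions; section 5.3 says that "interested women will fill out a contact sheet and make an appointment for the baseline session".

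On timing, section 7.0 states: "We will adjust analyses for baseline pregnancy stage and assessment timing". I found no visit window, no maximum gap between screening and baseline, and no rule that limits the week-8 indicator to days after baseline.

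**The concern.** A 90-day look-back taken 56 to 61 days after baseline still covers about a month before baseline. The entry rule selects women who had unprotected sex at about that time. One such day is enough for a 'yes', so the indicator can be settled before the intervention starts. A woman who stopped completely after HCEM would be recorded the same as one who changed nothing.

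Week 8 is also the time point of the primary outcome. A flat yes/no result there could be read as no effect on having any unprotected sex, when the measure had little room to show one.

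**Working it through.** **Inputs from the documents.** Look-back 90 days (5.5.2, 7.0); first follow-up at 8 weeks (day 56) or 2 months (day 60-61); second at 24 weeks (day 168); eligibility period 30 days (5.1); pilot mean 36 days of unprotected sex, taken as 36/90 = 0.40 per day (7.4); more than 95% 'yes' at baseline in the pilot and a 50% drop expected under HCEM (7.4); 100 per arm after dropout (7.4).

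**Assumptions.** Screening-to-baseline gap up to 45 days; daily rates vary between women as a beta distribution with concentration 0.5 to 5; carry-over is independent of later behaviour; two-sided 5% test.

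**1. The plan's own claim.** A 50% drop from 95% is 47.5%. For control I take 95% (no change) or about 90% (0.95 × 0.95 = 90.25%, the pilot's 5% reduction). With 100 per arm, power to separate 47.5% from either is above 99.9%. On true rates, the statement in 7.4 holds.

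**2. Overlap = 90 − visit day.**

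| Visit day | Pre-baseline days in window |
|---|---|
| 56 | 34 |
| 60 | 30 |
| 61 | 29 |
| 70 | 20 |
| 84 | 6 |
| 90 or later | 0 |
| 168 | 0 (window starts at day 78) |

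**3. Exact case.** With a gap of g days, the eligibility period ends g + 30 days before baseline. At day 56 it lies wholly inside the overlap if g + 30 ≤ 34, that is g ≤ 4. Every consistent reporter is then a 'yes', with no model needed.

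**4. Longer gaps.** Let P0(t) be the probability of no unprotected day in t days, w the overlap, and u the number of days in the overlap and eligibility period combined. Then carry-over is q = 1 − [P0(w) − P0(u)] / [1 − P0(30)].

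Example: day 56, gap 45, concentration 0.5. Here w = 34 and u = 64, with P0(34) = 0.2928, P0(64) = 0.2580 and P0(30) = 0.3003. So q = 1 − 0.0349/0.6997 = 95.0%.

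| Visit day | Carry-over, gaps 7-45 days |
|---|---|
| 56 | 95.0-99.9% |
| 61 | 94.3-99.6% |
| 70 | 92.2-98.5% |
| 84 | 80.5-87.3% |

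At half the pilot frequency, day 56 gives 91-99%. Other distributions (negative binomial and beta-binomial, calibrated to 5% with no day in 90) give 94.6-97.0% for days 56-61 at a 30-day gap, and 73-82% at day 84 for gaps up to 14 days.

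**5. Recorded rates at q = 95%.** Recorded rate = 1 − (1 − q)(1 − true rate).
- HCEM: 1 − 0.05 × 0.525 = 97.4%.
- Control: 1 − 0.05 × 0.10 = 99.5%, or 1 − 0.05 × 0.05 = 99.75%.

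**6. Between-arm power at week 8, 100 per arm, exact enumeration.** Each range runs from control 90% to control 95%.

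| Carry-over | Chi-square | Fisher |
|---|---|---|
| None | about 100% | about 100% |
| 80.5% | 72-87% | 62-79% |
| 87.3% | 50-68% | 35-48% |
| 95% | 17-21% | 3-4% |

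**7. The baseline level.** The baseline window is also 90 days, so every consistent reporter is 'yes' at baseline whenever g + 30 ≤ 90, that is g ≤ 60. The interaction needs some 'no' answers at baseline. At 95% 'yes', the chance that an arm of 100 has none is 0.95^100 = 0.6%. At 99% it is 0.99^100 = 37%, and at least one arm has none in 1 − (1 − 0.366)² = 60% of trials. At 100% the term has no finite estimate. Trimming the week-8 window does not change this.

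**The case against.** **The look-back.** The sentence in 5.5.2 can be read as giving 90 days to baseline only, with no stated look-back at 8 weeks. That reading is possible. Section 7.0 nevertheless uses one 90-day period for all its time points, so the two sections together favour a 90-day look-back throughout. If something shorter is meant, the plan should say so.

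**Visit timing.** Visits may run late. If Table 1's 19 to 28 weeks are gestational and baseline falls at 12 weeks (an assumption), the first follow-up falls between day (19 − 12) × 7 = 49 and day (28 − 12) × 7 = 112, and some visits have no overlap. This stands: the problem is worst on the nominal schedule and fades after it. Adjusting for assessment timing does not cure it, because a covariate cannot remove pre-baseline days from an outcome already recorded as 'yes'.

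**Stronger readings that a reader might infer.**
- That the planned mixed model has almost no power at week 8. This depends on how trials with an empty 'no' cell are scored, which the plan does not specify. A likelihood-ratio test that counts them gives about 22 to 25% at 95% carry-over in a simplified check with a 95% baseline and independent observations. That is low, but not nil.
- That trimming the window alone restores the planned test. That needs a baseline near 95%, whereas the entry rule pushes it towards 100%.
- That the 50% claim in 7.4 is wrong. It names no control rate, time point or window, so it is incomplete but not shown to be false.
- That the primary outcome fails. A count over a partly pre-baseline window is diluted but can still fall.

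**The pilot.** Its 27% against 5% reduction came from a 4-month assessment. A 90-day window there would start about 120 − 90 = 30 days after baseline, so it would have had no such overlap and gives no reassurance about week 8.

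**Conclusion.** The concern holds for one contrast: the yes/no unprotected-sex outcome at the first follow-up. For visits at days 56 to 61, about 94 to 100% of women are carried over as 'yes'. At 95% carry-over, between-arm power is about 17 to 21% (chi-square; 3 to 4% Fisher) for a true difference that would otherwise be detected almost surely. The same entry rule leaves baseline close to saturated, so the time-by-group term is poorly estimated even with a clean week-8 window.

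The overlap of 29 to 34 days is plain arithmetic once the 90-day look-back is accepted for all visits. The carry-over and power figures also rest on the assumed gaps, the spread of rates between women, and independence of carry-over from later behaviour. If women who stop had less frequent unprotected sex beforehand, fewer of them would be carried over. The 24-week contrast has no overlap. Because this is one time point of an additional analysis, I rate it minor to moderate.

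**What to change.** Make one change to section 7.0, in two parts:

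- **(a) Outcome window.** Define the week-8 yes/no unprotected-sex outcome on post-randomisation days only, with one fixed length for both arms (at most 56 days). Cut it from the Timeline Follow-Back data, which 5.5.2 describes as event-level, and state the rule for visits that occur before that length has elapsed.
- **(b) Comparison.** Compare arms at each follow-up with the baseline USO count as a covariate, instead of entering the near-saturated baseline yes/no status as an outcome level. Part (a) alone may not rescue the planned interaction test, so (b) belongs in the main change. The 24-week window can stay at 90 days.

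Recompute the binary power statement in 7.4 for the shorter window, and add the control rate, time point and window to which the 50% drop refers.

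The cost is plan wording, model code and that recalculation; no new data are needed. The downside is that week-8 proportions will not be directly comparable with baseline, 24 weeks or the pilot, so within-arm change from baseline to week 8 would mix window length with behaviour.
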